Appendix 5: Timeline

Month/Year Activities	June 2015	July 2015	August 2015	September 2015	October 2015	December 2015	June 2016	July 2016	August 2016
Contacting MoH, MoES, & YSMU		X							
Recruiting program coordinator	X								
Collect data about patients registered in polyclinics		X							
Recruiting trainers & supporting staff		X							
Training of supporting staff		X							
Trainers completing the online Edward Jenner Program			X						
Trainers complete the translation of educational materials			X						
Questionnaire pretest		X							
Baseline assessment			X						
Program implementation				X	X				
First follow-up assessment						X			
Second follow-up assessment							X		
Data entry			X			X	X		
Data analysis				X			X	X	
Final report writing									X

Appendix 6: Budget in Armenian Drams (AMD)

Budget Item	Type of appointment	Type of Appointment	Number of Units	Amount/Unit	Total
Personnel Fee					
Project Coordinator	Full Time	Fixed Monthly	14	150,000.00	2,100,000.00
Training Personnel (For taking the online Edward Jenner Program and translating the materials)	Fixed Hours (Flexible)	One Time	2	150,000.00	300,000.00
Training Personnel (For preparing and conducting the sessions)	Fixed Hours	Hourly	63*	10,000.00	630,000.00
Supporting Staff (For conducting the survey)	Flexible	Each Completed Questionnaire	1018	150.00	152,700.00
Supporting Staff (Transport compensation for conducting the survey)	Flexible	Day	90	400.00	3,600.00
Supporting Staff (Data Entry and Cleaning)	Part-Time	Hour	90†	1,500.00	135,000.00
Sub Total					3,321,300.00

* 63 Hours = (21 session) * (each session 1.5 hr.) * (two cohort)

† 90 Hours = (1080 questionnaires) * (5 Minutes/questionnaire)

Budget Item	Type of appointment	Type of Appointment	Number of Units	Amount/Unit	Total
Overhead Costs					
Administrative Costs					
Class Room Rentⁱ	Flexible Fixed Hours	Hourly	63	10,000.00	630,000.00
Office Room Rent	Full Time	Monthly	14	120,000.00	1,680,000.00
Paper Cost & Print	N.A	Per Piece	5000	10.00	50,000.00
Office Supplies	N.A.	N.A.	N.A.	100,000.00	100,000.00
Communication Costs					
Phone Land Line & Internet	Full Time	Monthly	14	15,000.00	210,000.00
Mobile Phone	Part Time	Monthly	3	5,500.00	16,500.00
Sub Total					2,686,500.00
Grand Total[#]					6,007,800.00

#Grand Total includes Income Tax and VAT

ⁱ 18 Person Seminar Room

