3.3.2 Study Settings and Target Population

In the intervention group, the target population is the family physicians' patients who have registered in the Heratsi polyclinic and attained treatment. In the comparison group, the target population is the family physicians' patients who have registered in the Muratsan Polyclinic and attained treatment. Heratsi and Muratsan polyclinics are selected for convenience; they both are under the administration of Yerevan State Medical University. Moreover, the organizational culture, administrative proceedings, pay scale, budgeting, and management are similar to each other. The inclusion and exclusion criteria of the survey participants are (Table 1):

Inclusion Criteria:

- a) Being registered with Heratsi or Muratsan polyclinics
- b) Being eighteen year old to sixty-five years old
- c) Visiting family physicians

Exclusion Criteria:

- a) Being registered with these polyclinics after the baseline assessment (exclusively for follow-up assessments)
- b) Patients who participated in the previous assessments in this survey (exclusively for follow-up assessments)

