3.3.3 Sampling Scheme

3.3.3.1 Sample Size

The student investigator calculated the sample size with the formula for two group comparison of means, exposed and unexposed groups for Cohort studies³⁶ by Epi-Info® -7 software. The outcome of the project is considered as a success if the difference between the intervening and comparison group in the first follow-up (O_1) assessment is 15% improvement in the patient-physician relationship percent score. From the existing literature of the other studies,³⁵ we assumed the baseline percent score of the patient-physician relationship to be 55.71% for both groups. After the intervention, the patient-physician relationship percent score is expected to increase to 64.07% in the intervention group in the first follow-up assessment (O_1).

The sample size is calculated based on the expected changes in the mean patient-physician relationship percent score in the intervention group of 15%. For variance, student investigator assumed that in both groups it will be equal. From a similar type of study,³⁵ the standard deviation of 2.5 was taken for calculation. Hence, the sample size was calculated to be one thousand one hundred and ninety eight (1198) in the intervention group and one thousand one hundred and ninety eight (1198) in the control group.

$$n_1 = n_2 = \frac{(Z\alpha/2 + Z\beta)^2 (\sigma_1^2 + \sigma_2^2)}{\Delta^2}$$

$$1198 = \frac{(1.96 + 1.28)^2 (2.5^2 + 2.5^2)}{(0.585)^2}$$

The literature shows that the response rate for similar types of evaluation studies have a response rate of 95%. Taking into consideration this information the estimated the sample size should be one thousand two hundred and sixty-two (1262) in each group.

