3.3.3.2 Sampling Scheme

For the selection of survey participants, the project team will use probability systematic random sampling. The survey will be conducted at the polyclinic as an exist survey, just after the patients' visit their family physicians. The survey will be conducted from Monday through Friday for 20 days. The survey hours will be from 09:00 to 13:00 in the respective months of the assessments in both polyclinics. The sample size for baseline and follow-up assessments each group in intervention and comparison is 1,262. To conduct the survey for 1,262 patients in twenty days, approximately sixty-four (64) surveys need to be conducted per day. The average numbers of patients visit the family physicians per weekday will be obtained (July 2015) from the administrators of the polyclinics. Then the interval between the survey participants will be calculated by dividing the number of visitors by nine for the baseline and follow-up assessments. After the patients' visit to the polyclinic, the supporting staff will approach to the patients. The patients, who have visited family physicians in the Heratsi and Muratsan polyclinics, will be asked to participate. The data will be collected through a self-administrated survey questionnaire. The supporting staff will collect the data from both polyclinics.

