3.3.2 Evaluation Study Design

The evaluation will consist of one baseline assessment and two follow-up assessments. The baseline assessment (**O₀**) of Patient-Physician Relationship percent score of the family physicians' patients of Heratsi and Muratsan Polyclinics will be gathered in August 2015. The follow-up assessment will be done one-month after the training in December 2015 (**O₁**) and seven months after the completion the program (six month after the first follow-up) in June 2016 (**O₂**). A Quasi-experimental, non-equivalent Control Group Design with independent groups will be applied for the proposed evaluation. The chosen design allows us to have a comparison group.

Intervention Group	O₀	X	O₁	O₂
Comparison Group	O₀		O₁	O₂

O₀ - Baseline Data Collection

X – Intervention

O₁ – Follow-up assessment one month after the end of the intervention

O₂ – Follow-up assessment six months after the first follow-up assessment

Threats to Internal Validity: History threat to internal validity will not be a significant issue since programs on leadership for family physicians Armenia are rare; moreover, having a comparison group will address the issue. Maturation can be a threat because the leadership development might not be only due to the intervention (Physician Leadership Development Program) but it might be due to the natural process of the physician acquired some skills during their practice; however, having a comparison group helps to address the issue. Testing cannot be a threat because the survey participants are independent. Instrumentation cannot be a threat, as the questionnaire used for the baseline and two follow-up assessments will be the same. Regression to the mean cannot be a threat because the survey participants are not people with only outlying characteristics related to the outcome variable of interest.

Selection bias can be a threat because there is no randomization of the survey participants into intervention and comparison groups. Moreover, the survey participants in both groups might differ from each other in terms of demographic and severity of disease. Compensatory rivalry can be a threat because the program participants will be aware of the evaluation study. Therefore, the family physicians might change their behavior and be friendlier with their patients. Attrition cannot be a threat because of survey participants are independent groups.

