3.3.5 Analysis

Once the supporting staff collects the data from survey participants, data entry will be carried out. In order to reduce the errors during the data entry, there will be cross checking of entered data by the project coordinator. The patient-physician relationship score from the questionnaire will be calculated into patient-physician relationship percent score.

Exploratory analysis will be done to clean the data by finding the missing values, outliers, and distribution of variables. Analysis will include descriptive analysis, independent T-test for continuous variables, Chi Square (χ^2) test for dichotomous variables, bivariate linear regression analysis and multivariate linear regression analysis.

4. Timeline

The proposed pilot project is planned to run for fourteen months, starting from June 2015 until August 2016. The physician leadership development program will be conducted for two months in the month of September and October 2015. The evaluation process will be conducted in three different duration, for baseline (O_0) and follow-up (O_1), (O_2) assessments (Appendix 5).

5. Budget

The total budget is estimated to be six million seven thousand eight hundred Armenian Drams (6,007,800.00 AMD) to implement this grant proposal (Appendix 6). The estimated budget for this grant proposal is calculated based on optimal fixed and overhead costs. The office and classroom for the program implementation, the classroom of 18 seating capacity is considered as an optimal. The rents are calculated as per AUA facilities' rental fees.⁴⁰ The costing is calculated for this proposal according to the average salaries for the personnel and type of services performed paid in the Armenian market as per May 2015.

6. Ethical Considerations

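### The budget covers 1,018 or 1,080 questionnaires, about 15% of the 7,188 the design implies, and matches a sampling interval of nine patients a day; transport is also understated tenfold

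*Protocol*

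**What the plan says.** **Sample.** Section 3.3.3.1 arrives at "one thousand one hundred and ninety eight (1198) in the intervention group", with the same number in the comparison group, and raises this to 1,262 for 95% response. Section 3.3.3.2 applies it at every round: "The sample size for baseline and follow-up assessments each group in intervention and comparison is 1,262". The section on evaluation study design states "The evaluation will consist of one baseline assessment and two follow-up assessments". The exclusion criteria for the follow-ups remove "Patients who participated in the previous assessments in this survey", so no respondent counts twice.

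**Fieldwork.** Section 3.3.3.2 allows 20 survey days per assessment and says about 64 surveys a day are needed. It then obtains the sampling interval by dividing the average weekday number of visitors by nine.

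**Budget.** Appendix 6 has three lines that depend on the survey:
- a fee to supporting staff per completed questionnaire: 1,018 at 150 AMD, printed as 152,700;
- data entry: 90 hours at 1,500 AMD, printed as 135,000, with the footnote "90 Hours = (1080 questionnaires) * (5 Minutes/questionnaire";
- "Supporting Staff (Transport compensation for conducting the survey": 90 days at 400 AMD, printed as 3,600.

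Section 5 repeats the sum: "The total budget is estimated to be six million seven thousand eight hundred Armenian Drams (6,007,800.00 AMD". There is no contingency line.

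**The concern.** Every completed questionnaire has to be collected and then entered, so the two lines should carry the same count, and that count should be the planned sample over both polyclinics and all three assessments. Neither holds. The gap is far too large for rounding or non-response.

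The figure in the data-entry footnote also fits the sampling interval and not the stated sample size. That suggests two incompatible sample sizes in one document: 1,262 per cell in the sample-size text, and about 180 per cell in the field procedure and the budget (a cell being one polyclinic at one assessment). Staff who followed the interval literally would collect about one seventh of the stated sample. Because the document is a grant proposal, its total is the amount requested, and that amount does not pay for the stated sample.

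**Working it through.** **1. Reproduce the plan's total.**
- Personnel: 2,100,000 + 300,000 + 630,000 + 152,700 + 3,600 + 135,000 = 3,321,300, as printed.
- Overhead: 630,000 + 1,680,000 + 50,000 + 100,000 + 210,000 + 16,500 = 2,686,500, as printed.
- Sum: 6,007,800, as printed.

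The subtotal adds up only with 3,600 for transport, so that figure is not a text-extraction fault.

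**2. Check units times price on the three survey lines.**
- Survey fee: 1,018 × 150 = 152,700. Correct.
- Data entry: 1,080 × 5 / 60 = 90 h; 90 × 1,500 = 135,000. Correct.
- Transport: 90 × 400 = 36,000, printed as 3,600. Difference 32,400; 32,400 / 6,007,800 = 0.5%.

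**3. Questionnaires the design needs.** Cells = 2 polyclinics × 3 assessments = 6.
- Completed: 6 × 1,198 = 7,188. Approached: 6 × 1,262 = 7,572.
- Paid for: 1,018 / 7,188 = 14.2%. Entered: 1,080 / 7,188 = 15.0%.

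Smaller readings do not close the gap. If 1,198 were the total per group over all three rounds, the need would be 2 × 1,198 = 2,396. With the number the printed formula actually gives, (1.96 + 1.28)² × (2.5² + 2.5²) / 0.585² = 10.4976 × 12.5 / 0.342225 = 383.4, so 384 per cell, the need would be 6 × 384 = 2,304. Both are more than twice 1,080.

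**4. Where 1,080 fits.**
- Nine a day: 9 × 20 × 2 × 3 = 1,080, or 180 per cell.
- Sixty-four a day: 64 × 20 × 2 × 3 = 7,680, consistent with 1,262 / 20 = 63.1 a day, rounded up.

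**5. Re-price at the plan's own unit costs.** Lines that do not change: 6,007,800 − 152,700 − 135,000 − 3,600 = 5,716,500.

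| Completed questionnaires | Survey fee | Data entry | Transport (90 days) | Grand total | Change |
|---|---|---|---|---|---|
| 7,188 | 1,078,200 | 599 h = 898,500 | 36,000 | 7,729,200 | +1,721,400 (+29%) |
| 2,304 | 345,600 | 192 h = 288,000 | 36,000 | 6,386,100 | +378,300 (+6%) |

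Correcting transport alone gives 6,040,200. Printing is left as budgeted.

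**6. Power if only the budgeted number were collected.** Power = Φ(Δ / (σ√(2/n)) − 1.96).
- With the formula's Δ = 0.585 and σ = 2.5: n = 180 gives Φ(2.22 − 1.96) = 60%; n = 1,018 / 6 ≈ 170 gives Φ(2.16 − 1.96) = 58%. The plan's z of 1.28 corresponds to 90%.
- With the rise also stated in Section 3.3.3.1, 64.07 − 55.71 = 8.36 points, and σ = 2.5 read in points: power is essentially 100% at either n.

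**The case against.** The strongest reply is that these are administrative lines in an appendix. The budget is called an estimate, no endpoint or analysis depends on it, and nothing says that collection stops when the survey line is spent. That is fair, and it limits the consequence. It does not remove the contradiction, because the same 180 per cell appears in the sampling procedure, which fieldworkers would follow.

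Four stronger readings are tempting, and the document does not support them.
- *The study will have 58–60% power.* This needs the budget or the interval to be binding, and it needs 0.585 with SD 2.5 to be the right inputs. Section 3.3.3.1 also states an 8.36-point rise and gives no unit for the SD. If the SD is in points, power at 180 per cell is ample.
- *Ninety transport days is too few, because 20 × 3 × 2 = 120.* The line says only that the unit is a day. It gives neither the number of staff nor whether payment is per site, so no error in the day count is shown.
- *The 5,000 printed pieces are too few.* A piece is not defined as a sheet or a questionnaire. Counted as questionnaires, 5,000 falls short of 7,188 but exceeds 2,304.
- *The transport slip is why the sample cannot be funded.* It is 0.5% of the total. The questionnaire count accounts for nearly all of the shortfall.

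Two further cautions stand. The 7,188 is derived here and is not printed in the protocol. That 1,080 and the divisor of nine are left over from a smaller sample size is an inference from an exact numerical match.

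**Conclusion.** The point holds as an inconsistency that should be corrected. The budget contradicts itself (1,018 against 1,080) and covers about 15% of the questionnaires the design implies. It agrees with the sampling interval while disagreeing with the 64 a day and the 1,262 in the same section. The transport line is wrong by 32,400 AMD, and the error passes into the personnel subtotal and the grand total.

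The funding shortfall is 1,721,400 AMD (29%) at 1,198 completed per cell, or 378,300 AMD (6%) at 384. Both figures assume the plan's unit prices, six independent samples, payment per completed questionnaire, 90 transport days, and no change in printing. The 180-per-cell reading assumes that the visitor count divided by nine is each polyclinic's own weekday average. An effect on power is possible but is not established by the document.

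**What to change.** 1. Settle one sample size per polyclinic and assessment. Section 3.3.3.1 has to be put right first, since its printed formula gives 384 and not 1,198. If a larger size is then chosen for other design reasons, carry that one forward.
2. Set the daily quota and the interval divisor in Section 3.3.3.2 from that size, so that the two agree. For 1,262 approached the divisor is about 64. For 384 completed it is about 21 (384 / 0.95 = 404.2, so 405 approached; 405 / 20 = 20.25).
3. Use the resulting single count of completed questionnaires in both the survey-fee and the data-entry lines.
4. Correct transport to 36,000 AMD for 90 days, and restate the personnel subtotal and the grand total in Appendix 6, Section 5 and the Executive Summary.
5. In the same pass, define the transport day and the printed piece, and confirm that both quantities suit the chosen size.

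The editorial cost is one recalculated table and a few sentences. The request rises by about 0.4 million AMD at 384 per cell, or about 1.7 million AMD at 1,198, before any change in printing.
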